Enhanced recovery pathways, patient-reported outcomes and return to intended oncological therapy after colorectal surgery: the Italian ColoRectal Anastomotic Leakage study group (iCral 3).

BACKGROUND

The ultimate goal of any surgery is to return the patient to at least their baseline functional status, if not an improved functional status compared with their preoperative state, as rapidly as possible and with the least amount of intercurrent disability. Enhanced Recovery After Surgery (ERAS) is a multimodal and multifactorial approach to the optimization of perioperative management (1, 2). In order to modify and improve the response to surgery-induced trauma, the program relies on a series of evidence-based items related to pre-, intra- and post-operative care (3). Several meta-analyses on ERAS showed a significant reduction of morbidity rates and length of stay after colorectal surgery (4-6). However, program implementation outside clinical trials is still extremely variable (7-9), as the necessary multidisciplinary involvement makes the program vulnerable to various areas of failure, that explain the great variation in adherence rates to program items (10-12).

During the early phase of program implementation, adherence rate to program items rarely goes beyond 50% (13), needing to reach at least 70% in order to significantly improve results (faster recovery and reduced morbidity). A recent cohort study conducted in 80 Spanish centers on about 2,000 patients recruited in 2 months (14) reported a mean adherence rate to ERAS items at 63.6%, reaching 72.7% in centers that declared to have an institutional program. A large multicenter study conducted on 2,352 patients undergoing colorectal resection in 13 centers in 6 different European countries also showed a mean overall adherence rate to ERAS items at 75% (15). In other studies, adherence to ERAS items was higher, reaching up to 90% (16, 17).

Moreover, a clear and significant dose-effect curve between adherence rate to ERAS program items and early outcomes was demonstrated (18-20), and recent evidence deriving from retrospective studies suggests that ERAS programs may also offer a definite advantage over long-term survival after colorectal resection for malignancy (21-23). While many studies to date have focused on early outcomes (i.e. earlier return of bowel function, lower complication rates, and/or shorter length of inpatient stay), for the majority of oncologic operations, however, postoperative recovery carries the additional demand of returning the patient to adjuvant oncologic therapies. It is still unclear if ERAS program could improve the failure to “return to intended oncologic therapy” (RIOT) after cancer surgery due to complications and lingering poor performance status (24), that is strongly associated with worse oncologic outcomes, including shortened overall survival (25, 26). Measuring patient-reported outcomes (PROs) addresses the gap in enhanced recovery assessment by incorporation of patient-centered quality into our global assessment of outcomes (27). Taken together, these data establish a paradigm for association of perioperative medical care to long-term oncologic outcomes—revealing how the perioperative care team’s actions over a relatively short number of days and hours around the time of a cancer surgery can improve cancer-specific survival. The concept is that various perioperative techniques, protocols, and agents will blunt the patient’s perioperative stress response, reduce complications, and improve functional recovery after surgery. Together, these effects allow more people to RIOT in a more timely fashion and in a more complete way. To the extent that the combination of preservation of immune competence and more reliable return to adjuvant therapies then reduce recurrence rates, longer and more meaningful survivals may be achieved.

Therefore, we planned this study to prospectively evaluate the impact of adherence to ERAS program items after colorectal resections on PRO in the whole population and on failure to RIOT for malignant disease.

METHODS

Prospective enrollment from November 2020 to October 2021 in 60 Italian surgical centers. All patients undergoing elective or delayed urgency colorectal surgery with anastomosis will be included in a prospective database after written informed consent. A total of 3,000 patients is expected based on a mean of 50 cases per center.

Inclusion criteria

1. Patients submitted to laparoscopic/robotic/open/converted ileo-colo-rectal resection with anastomosis, including planned Hartmann's reversals.
2. American Society of Anesthesiologists' (ASA) class I, II or III
3. Elective or delayed urgency surgery
4. Patients' written acceptance to be included in the study.

Exclusion criteria

1. American Society of Anesthesiologists' (ASA) class IV-V
2. Emergent surgery
3. Pregnancy
4. Hyperthermic intraperitoneal chemotherapy for carcinomatosis.

Outcome measures

1. Preoperative risk factors for morbidity (age, gender, obesity, nutritional status, diabetes, cardiovascular disease, chronic liver disease, renal failure, inflammatory

bowel disease, perioperative steroid therapy, ASA class I-II vs III, SARS-CoV-2 infection)

2. Operative parameters (approach, procedure, anastomotic technique, length of operation, pTNM stage)
3. Adherence to ERAS program (28, 29) items (Tab.1).

Endpoints

Primary

1. Patient-related outcomes measures (PROMs):
 - a. Euro-QoL Group EQ-5D-5L (EQ-5D-5L, 32);
 - b. MD Anderson Symptom Inventory for gastrointestinal surgery patients (MDASI-GI, 33);
 - c. Functional Assessment of Cancer Therapy – Colorectal (FACT-C, 34)
2. Return to intended oncologic therapy (RIOT, 24)

Secondary

3. Anastomotic leakage rate
4. Minor and major complication rates according to Clavien-Dindo (35, 36) and JCOG (37) classification
5. Overall length of postoperative hospital stay (including any readmission)
6. Difference between date of readiness for discharge (RFD, 38) and date of actual discharge
7. Readmission and reoperation rates
8. Comparison of two nutritional status scores, MNA-SF (30) and PNI (31), regarding anastomotic leakage, minor and major complication rates and RIOT (24)

9. Impact of anastomotic testing through air-leak test (ALT) and near-infrared fluorescence (NIR) narrow-band imaging (NBI) using indocyanine green (ICG) on anastomotic leakage rates

Recorded data and follow-up

Potential patient-specific and intraoperative risk factors will be recorded: gender, body mass index, nutritional status, frailty (39), surgical indication (cancer, polyps, chronic inflammatory bowel disease, diverticular disease), use of steroids, renal failure and dialysis, cardiovascular or respiratory disease, American Society of Anesthesiologist class, bowel preparation, type of approach, level of anastomosis and technique (mechanical or hand-sewn, intra- or extra-corporeal), operative time, presence of drainage, and perioperative blood transfusion(s). During the postoperative period, patients will be examined by the attending surgeon daily. Fever (central temperature > 38 °C), pulse, abdominal signs, bowel movements, volume and aspect of drainage (if present) will be recorded daily. The local attending surgeon will make any decision for complementary exams and imaging according to his own criteria, the only exception being the creation of a proximal diverting stoma at operation, that mandates routine check of anastomotic integrity through an intraluminal contrast exam (standard x-rays or CT scan), MRI, or direct endoscopic evaluation three to six weeks after the operation. The rate of any adverse event will be calculated and graded according to Clavien-Dindo criteria (35, 36) and to Japan Clinical Oncology Group Postoperative Complications (JCOG-PC) extended criteria (37), including all anastomotic leaks, wound infection (according to the definitions of the Centers for Disease Control and Prevention and wound culture, 40), pneumonia (clinical symptoms, and physical and radiological examinations), central line infection (positive blood culture), urinary tract infection (positive urine

culture with bacterial count). Patients will be followed-up in the outpatient clinic up to 8 weeks after discharge from the hospital.

Anastomotic dehiscence (any deviation from the planned postoperative course related to the anastomosis, or presence of pus or enteric contents within the drains, presence of abdominal or pelvic collection in the area of the anastomosis on postoperative CT scan, leakage of contrast through the anastomosis during enema or evident anastomotic dehiscence at reoperation for postoperative peritonitis) will be defined and graded according to international consensus guidelines (41). Anastomotic testing will be performed intraoperatively with the air-leak test (ALT) and using ICG-NIR-NBI with a standard protocol [*ICG 25 mg diluted in 10 mL water (2.5 mg/mL); first bolus i.v. injection of 4 mL (10 mg) after vascular control and mesenteric division, just before proximal and/or distal bowel division; second bolus i.v. injection of 4 mL (10 mg) just before joining anastomotic stumps; third (optional) bolus i.v. injection of 2 mL (5 mg) after the anastomosis is completed; NIR-NBI observation within 120-180" after every ICG injection (direct, laparoscopic or endoscopic)*].

PROM questionnaires (32-34) will be administered to all enrolled patients four to one week before the planned operation, on the day of discharge, and 6 weeks after the operation.

RIOT (24) rates will be recorded in all patients submitted to surgery for malignancy, according to national guidelines for colorectal cancer (42).

After anonymization, all data of each single case will be prospectively uploaded by local investigator(s) on a protected web-based database and incorporated into a spreadsheet for data analysis, checking for any discrepancy, that will be addressed and solved through strict cooperation between chief investigator, data manager and participating centers.

Ethics and dissemination

The study will be conducted according to the Helsinki declaration and to the Guideline for good clinical practice E6(R2) principles. This study protocol will be submitted to the coordinating
ALL 3 – Protocollo dello Studio

center ethics committee (Comitato Etico Regionale delle Marche - C.E.R.M.) for approval and then registered at ClinicalTrials.gov (NCT04397627). Thereafter, all the participating centers will obtain authorization to participate from the local institutional review board. The results of the study are intended to be presented at national and international medical congresses on corresponding fields of interest (colorectal surgery, abdominal surgery). Written publications of the results are planned within surgical journals. The authorship for written publications is confirmed to all participating investigators, only being granted in the case of substantive contributions to the design, conduct, data analysis, collection and interpretation. Anonymized participant-level datasets will be available after study completion upon reasonable request by contacting the principal investigator.

Statistical Analysis

Quantitative values will be expressed as mean \pm standard deviation (SD), median and range; categorical data with percentage frequencies. For categorical data, analysis will include the use of cross tabulation, chi squared or Fisher's exact test where indicated. Continuous or discrete variables will be analyzed using Student's two-sided t test (allowing for heterogeneity of variances) or with a non-parametric test (Mann-Whitney U test or Kruskal-Wallis test as indicated). Joint and conditional multivariate association between all variables shown to be significant on univariate analysis will be assessed using binary logistic or multiple linear regression. The odds ratio (OR) will be presented followed by 95% confidence interval (95% CI). Concerning comparison of nutritional status scores, areas under the receiver-operating characteristics curve (AUC-ROC) will be calculated for all endpoints, considering values from 0.7 to 0.8 as acceptable, 0.8 to 0.9 excellent, and above 0.9 as outstanding (43). Differences in AUC-ROC curves will be analyzed with the chi-squared test. Optimal cut-off points will be obtained applying Youden's Index (Sensitivity+Specificity-1), choosing those values of the AUC-ROC curve where this index is

maximal. Negative predictive values (NPV) and positive predictive values (PPV) will also be calculated; finally, a logistic regression model will be built using the presence/absence of endpoint as dependent variable, and nutritional scores \leq or $>$ the cut-off values as explanatory factors; using logistic transformation of the linear predictors, the probabilities of the endpoint related to the different combinations of factors level will be obtained (44). For all statistical tests the significant level is fixed at $p < .05$. Statistical analyses will be carried out using STATA software (Stata Corp. College Station, Texas, USA).

Sample size

Adherence to at least 70% of the ERAS program items was identified as a cut-off for significant improvement of outcomes (18), with a 2:1 expected ratio below:above the cut-off. Estimating a reduction of postoperative PRO from preoperative baseline (1.0) at 0.7 for adherence above the cut-off and at 0.64 for adherence below the cut-off (44), alpha 0.04, beta 0.8, the required sample size is $n=2,406$ (802 cases above 70% adherence and 1,604 below 70% adherence). Reported rates for failure to RIOT and ERAS program items adherence below or above 70% are 13 and 6.5%, respectively (27); the required sample size for evaluation of failure to RIOT is $n=885$ (295 cases above 70% adherence and 590 below 70% adherence). Based on previous iCral observational study on colorectal surgery in Italy (44, 46, 47), the expected ratio of malignant:benign indications to surgery is 70:30 (2,100 resections for malignancy and 900 resections for benign disease on the basis of 3,000 expected cases).

References

2. Kehlet H (2008) Fast-track colorectal surgery. *Lancet* 371:791–793.

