[name], FACS
iCral study group coordinator
Chief investigator

Acronyms

ALT: Air leak test

ASA: American Society of Anesthesiologists

EQ-5D-5L: Euro-QoL Group EQ-5D-5L

ERAS: Enhanced Recovery after Surgery

FACT-C: Functional Assessment of Cancer Therapy – Colorectal

ICG: indocyanine green

JCOG: Japan Clinical Oncology Group

JCOG-PC: Japan Clinical Oncology Group Postoperative Complications

MDASI-GI: MD Anderson Symptom Inventory for gastrointestinal surgery patients

MNA-SF: mini nutritional assessment – short form

MRI: magnetic resonance imaging

NBI: narrow-band imaging

NIR: near-infrared

PNI: prognostic nutritional index

PROs: patient-reported outcomes

PROMs: patient-reported outcomes measures

RFD: readiness for discharge

RIOT: return to intended oncologic therapy

Tab. 1: Definition of adherence to ERAS program items (28, 29).

	ITEM	Adherence criteria
Preoperative	Nutritional status screening	Patient submitted to nutritional screening through Mini Nutritional Assessment Short Form (MNA-SF) (30) and Prognostic Nutritional Index (PNI) (31)
	Nutritional Prehabilitation	All patients showing MNA-SF < 12 (malnourished or suspect for malnutrition) and BMI > 30 (obesity) receive specific nutritional consultation
	Physical Prehabilitation	Patient receives a standard protocol of physical activity to be accomplished in the preoperative period; frail and limited motility patients are submitted to specific geriatrician/physiatrist consultation and personalized activity program
	Psychologic Prehabilitation	Patient and his familiars/caregivers are screened by the case-manager; in case of anxiety/depression concerning diagnosis and related procedure psychologic consultation is warranted
	Counseling	Patient and his familiars/caregivers receive full information and suggestions regarding perioperative program from surgeon, anesthesiologist and case-manager
	Preoperative Immunonutrition	Patient is administered Impact Oral™ (Nestlè Health Science, Italy) 330 ml per os, three briks per day during 5 days preceding surgery or two briks per day during 7 days preceding surgery
	Management of anemia	Patient with Hb concentration < 130 g/L for men and <120 g/L for nonpregnant women receive correction of anemia before surgery preferably through intravenous iron preparations (ferric carboxymaltose) and blood transfusion(s) in strictly necessary cases

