Appendix 1 CLAVIEN-DINDO CLASSIFICATION (35, 36)

Grade	Definition
Grade I	Any deviation from the normal postoperative course without the need for pharmacological treatment or surgical, endoscopic, and radiological interventions. Allowed therapeutic regimens are: drugs as antiemetics, antipyretics, analgetics, diuretics, electrolytes, and physiotherapy. This grade also includes wound infections opened at the bedside
Grade II	Requiring pharmacological treatment with drugs other than such allowed for grade I complications. Blood transfusions and total parenteral nutrition are also included
Grade III	Requiring surgical, endoscopic or radiological intervention
Grade IIIa	Intervention not under general anesthesia
Grade IIIb	Intervention under general anesthesia
Grade IV	Life-threatening complication (including CNS complications)* requiring IC/ICU management
Grade IVa	Single organ dysfunction (including dialysis)
Grade IVb	Multiorgan dysfunction
Grade V	Death of a patient

*Brain hemorrhage, ischemic stroke, subarachnoidal bleeding, but excluding transient ischemic attacks. CNS, central nervous system; IC, intermediate care; ICU, intensive care unit.

Grades	Organ System	Examples
Grade I	Cardiac	Atrial fibrillation converting after correction of K ₊ -level
	Respiratory	Atelectasis requiring physiotherapy
	Neurological	Transient confusion not requiring therapy
	Gastrointestinal	Noninfectious diarrhea
	Renal	Transient elevation of serum creatinine
Grade II	Other	Wound infection treated by opening of the wound at the bedside
	Cardiac	Tachyarrhythmia requiring β -receptor antagonists for heart rate control
	Respiratory	Pneumonia treated with antibiotics on the ward
	Neurological	TIA requiring treatment with anticoagulants
	Gastrointestinal	Infectious diarrhea requiring antibiotics
Grade IIIa	Renal	Urinary tract infection requiring antibiotics
	Other	Same for I followed by tx with antibiotics for phlegmonous infection
	Cardiac	Bradyarrhythmia requiring pacemaker implantation in local anesthesia
	Neurological	See grade IV
	Gastrointestinal	Biloma after liver resection requiring percutaneous drainage
Grade IIIb	Renal	Stenosis of the ureter after kidney transplantation treated by stenting
	Other	Closure of dehiscient noninfected wound in the OR under local anesthesia
	Cardiac	Cardiac tamponade after thoracic surgery requiring fenestration
	Respiratory	Bronchopleural fistulas after thoracic surgery requiring surgical closure
	Neurological	See grade IV

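### Transfusion is listed as a risk factor with no time limit, while a postoperative transfusion is itself a grade II complication, so its association with overall and minor complications can be partly true by definition

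*Protocol*

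**What the plan says.** The Protocol, in the section on recorded data and follow-up, opens its list of covariates with "Potential patient-specific and intraoperative risk factors will be recorded" and ends it with "operative time, presence of drainage, and perioperative blood transfusion(s". No start or end point is given for the transfusion item.

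Under Endpoints, the fourth item is "Minor and major complication rates according to Clavien-Dindo (35, 36) and JCOG (37) classification", a secondary endpoint. The follow-up section adds "The rate of any adverse event will be calculated and graded according to Clavien-Dindo criteria (35, 36" and does not exempt transfusion.

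Appendix 1 sets the frame of the scale in grade I, "Any deviation from the normal postoperative course without the need for pharmacological treatment", and says of grade II: "Blood transfusions and total parenteral nutrition are also included".

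The Statistical Analysis section states the modelling rule: "Joint and conditional multivariate association between all variables shown to be significant on univariate analysis" is to be assessed by binary logistic or multiple linear regression.

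Transfusion before surgery is also foreseen. In Tab. 1 the anaemia item allows "blood transfusion(s) in strictly necessary cases" as part of preoperative correction.

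**The concern.** Take a patient whose only untoward event is a transfusion on the second day after surgery. If the field is filled in as worded, that patient is exposed to the risk factor. Under Appendix 1 the same patient has a grade II complication. Nothing has been predicted, because one event has been entered on both sides of the model.

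The study could then report transfusion as an independent risk factor for complications even if it had no effect, and the selection rule would help, since such a variable tends to pass a univariate screen. For leakage and for grade III or higher complications the difficulty is different: a transfusion given after the event is a consequence of it and cannot be a predictor.

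**Working it through.** **1. Is there an overlap in the text?** Four places matter.

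- *Exposure* (Recorded data and follow-up): perioperative transfusion, no window.
- *Outcome* (Endpoints; Recorded data and follow-up): complication rates, with all adverse events graded.
- *Grading* (Appendix 1): transfusion is grade II, on a scale defined against the postoperative course. Transfusion before or during surgery is therefore outside the scale, and postoperative transfusion is inside it.
- *Link* (Statistical Analysis): all variables significant on univariate analysis go into the model, with no exception for transfusion.

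The overlap is thus confined to postoperative units, and it exists only if these are counted as exposure.

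**2. How large is the built-in odds ratio?** The Protocol states no figure to reproduce, so this is an illustration. Assumptions: transfusion has no effect; other complications occur at rate b in transfused and untransfused patients alike; a share s of transfused patients received units after surgery and so have a complication by definition.

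- Risk if transfused: s + (1-s)b
- Risk if not transfused: b
- Odds if transfused: [s + (1-s)b] / [(1-s)(1-b)]
- Odds if not transfused: b/(1-b)
- Odds ratio: [s + (1-s)b] / [(1-s)b] = 1 + s/((1-s)b)

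Example with b = 0.20 and s = 0.50: risk 0.50 + 0.50 × 0.20 = 0.60, odds 1.5, against odds 0.25, so the odds ratio is 6.0.

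| s | b = 0.20 | b = 0.25 | b = 0.30 |
|---|---|---|---|
| 0 | 1.0 | 1.0 | 1.0 |
| 0.10 | 1.56 | 1.44 | 1.37 |
| 0.25 | 2.67 | 2.33 | 2.11 |
| 0.50 | 6.0 | 5.0 | 4.33 |
| 0.75 | 16.0 | 13.0 | 11.0 |

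The result does not depend on how many patients are transfused. A simulation with s = 0.50 and b = 0.25 gave 5.0 with the overlap and 0.99 without it.

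The formula is for overall complications. For minor complications alone the figure also depends on how patients with higher-grade events are classed. Reading minor as grade I-II is itself an assumption, since the Protocol does not spell it out.

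**3. Would transfusion reach the multivariable model?** With the 3,000 patients expected in the Protocol, 5% to 10% of them transfused (assumed) and its significance level of .05, the chance of passing the univariate screen with no real effect is:

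- s = 0.10: 64% to 88% for b = 0.20, and 45% to 70% for b = 0.30
- s = 0.25 or more: at least 99% for either b

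**The case against.** The list is headed as patient-specific and intraoperative, and the postoperative observations start in a separate sentence. On that reading the item means units given before or during surgery, s is zero and nothing is wrong. This has some force, but it does not settle the window. The Background describes enhanced recovery as perioperative management made up of pre-, intra- and postoperative items, so the Protocol's own use of the word includes the time after surgery. With 60 centres entering data, an item broader than its heading will not be read in one way.

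It is also fair that the list only says the factors are recorded and names no outcome for them, and that transfusion is absent from the formal Outcome measures. The model is an inference. It is the natural one: the Outcome measures speak of risk factors for morbidity, the regression rule covers all significant variables, and the title of reference 47, an earlier paper of the study group, joins risk factors for adverse events with blood transfusion.

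A statistical analysis plan, which is not shown, may fix the window. It could separate exposure from outcome only if timing was collected. The text at hand asks for no transfusion date, though the case form is not shown and may hold one.

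A reader might go further and infer that leakage, major complications, length of stay, the patient-reported measures or return to oncologic therapy are distorted in the same way. The documents do not support that: none of these contains transfusion by definition. Nor do they support a claim that transfusion is bound to pass the screen, which holds from about s = 0.25 but not at s = 0.10. That transfusion would draw effect away from adherence in a joint model is possible, but no figure here shows it.

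**Conclusion.** The point holds for overall and minor complications, a secondary endpoint, and to the extent that postoperative units count as exposure. The Protocol as worded allows this, and its modelling rule carries the result forward. It does not state an intention to use postoperative transfusion as a predictor.

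The size rests on two assumed quantities. Over b = 0.20 to 0.30 the spurious odds ratio runs from 1.0 if no transfused patient was transfused after surgery to between 11 and 16 if three quarters were. Even a quarter gives 2.1 to 2.7, enough to be reported as an independent risk factor. For leakage and grade III or higher complications the remaining issue is the order of events, for which no size can be given. The primary endpoints are not affected by definition, and the sample size is untouched. This should be corrected, but it does not threaten the main comparison.

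**What to change.** In the section on recorded data and follow-up, define the risk factor as transfusion before or during the operation. Record postoperative transfusion as a separate item with its date. State in the Statistical Analysis section that postoperative transfusion is not an explanatory variable in models of complications or leakage. As an alternative for the overlap, leave grade II events that consist only of a transfusion out of the endpoint in any model that contains transfusion; this does not resolve the order of events for leakage and major complications.

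With s = 0 the built-in odds ratio returns to 1.0. The overlap gives no reason to extend the exclusion to models of stay, patient-reported outcomes or return to oncologic therapy; that would need its own argument.

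The cost is a sentence or two in the Protocol and, if the case form does not already separate transfusions by timing, one split field. The downside is that fewer transfused patients remain for the risk-factor estimate, so it will be less precise. The change is best made before data entry, because timing may not be recoverable afterwards. No patient's care is altered.

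### Complication surveillance is denser before discharge and its window runs from discharge, so minor-complication rates compared by ERAS adherence are open to differential detection of unknown size

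*Protocol*

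**What the plan says.** Recorded data and follow-up describes two phases of observation.

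- **Postoperative period.** "During the postoperative period, patients will be examined by the attending surgeon daily". Temperature and pulse are also noted, and "abdominal signs, bowel movements, volume and aspect of drainage (if present) will be recorded daily".
- **After discharge.** "Patients will be followed-up in the outpatient clinic up to 8 weeks after discharge from the hospital". The protocol gives no number or dates of visits and no standard set of complication questions.

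Further tests are discretionary: "The local attending surgeon will make any decision for complementary exams and imaging according to his own criteria". The one stated exception is a check of the anastomosis at three to six weeks in patients with a diverting stoma.

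The affected outcome is secondary endpoint 4: "Minor and major complication rates according to Clavien-Dindo (35, 36) and JCOG (37) classification". In Appendix 1 the lowest grade is "Any deviation from the normal postoperative course without the need for pharmacological treatment or surgical, endoscopic, and radiological interventions". Its examples include transient confusion, noninfectious diarrhea and a transient creatinine rise. The Background cites meta-analyses in which ERAS reduced length of stay.

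**The concern.** Intensity of observation changes at discharge, and the day of discharge is expected to depend on the exposure. Patients with high adherence should go home sooner and so leave daily examination sooner. On the days when one group is at home and the other still in hospital, the same mild event may be written down in one group and go unnoticed in the other.

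Grade I events are the most exposed. They need no treatment, so they rarely bring a patient back, and recording "Readmission and reoperation rates" will not pick them up. The chi-squared or Fisher tests and the logistic regression in Statistical Analysis cannot recover events that were never recorded. The study could then credit ERAS adherence with a reduction in minor morbidity that comes partly from how events were found.

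**Working it through.** The protocol states no figure on this point. It gives no length of stay in days, no minor-complication rate, no timing of complications and no sensitivity of detection. The direction follows from the text, but the size can only be illustrated.

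**Inputs from the protocol.** There are 3,000 expected patients with a 2:1 split below:above 70% adherence (Sample size), so 3,000 × 1/3 = 1,000 high-adherence and 2,000 low-adherence patients. The test level is 0.05 (Statistical Analysis).

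**Assumed inputs.**
- True minor-complication rate p, equal in both groups: 15% or 25%.
- Share q of minor events arising between the earlier and the later discharge: 15% or 30%.
- Detection in hospital: 100%.
- Detection after discharge, s: varied from 40% to 100%.

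**Coverage.** With assumed stays of 4 and 7 days, daily examination covers 4/7 = 57% of the first week in one group and 7/7 = 100% in the other. The total windows are 4 + 56 = 60 and 7 + 56 = 63 days. The extra days fall some two months after surgery, so the density of observation is likely to matter more than its length.

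**Spurious difference.** Difference = p × q × (1 − s). The observed high-adherence rate is p minus this difference, and the observed low-adherence rate is p. The rejection probability is for a two-sided two-proportion z test with 1,000 versus 2,000 patients.

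Worked extremes:
- p = 0.25, q = 0.30, s = 0.4: 0.25 × 0.30 × 0.6 = 0.045. The rates are 20.5% and 25%; OR = (0.205/0.795)/(0.25/0.75) = 0.77.
- p = 0.15, q = 0.15, s = 0.9: 0.15 × 0.15 × 0.1 = 0.00225. The rates are 14.775% and 15%; OR = 0.98.

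| Detection after discharge | Spurious difference (points) | False OR | Chance of p < 0.05 |
|---|---|---|---|
| 100% | 0 | 1.00 | 5% |
| 90% | 0.23–0.75 | 0.98–0.96 | 5–7% |
| 70% | 0.68–2.25 | 0.95–0.88 | 8–27% |
| 40% | 1.35–4.50 | 0.90–0.77 | 16–79% |

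**Variant.** Suppose that a further 20% of events arise after both groups have gone home, and let q run from 10% to 30%. The observed rates become p × [1 − (q + 0.2)(1 − s)] and p × [1 − 0.2(1 − s)]. The false OR is then 0.96–0.99 at s = 90%, 0.88–0.96 at 70% and 0.80–0.94 at 50%. The direction is unchanged and the size similar.

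**The case against.** A reader might infer that earlier discharge lowers the recorded minor rate by construction. The documents do not support that. Every patient has outpatient follow-up, the protocol grades adverse events without limiting them to the hospital stay, readmissions and reoperations are recorded, and all patients complete questionnaires six weeks after the operation. If post-discharge detection were complete there would be no bias. That daily examination ends at discharge is itself an inference, though hard to avoid, since daily examination by the attending surgeon cannot reasonably describe patients at home.

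Four further objections have force.
- **Magnitude.** Apart from the patient numbers, the split and the test level, every input is assumed. The upper end of the table reflects the choice of inputs and is not a finding about this study.
- **Reverse causation.** Complications prolong stay, and the pre-discharge check in Tab. 1 looks for their absence. Part of any link between early discharge and few complications therefore has nothing to do with detection. This is a separate problem and does not remove the first.
- **Examples.** A transient creatinine rise is found by a blood test, not by the daily signs listed, and tests are at the surgeon's discretion.
- **Scope.** The stated aim concerns patient-reported outcomes and failure to return to oncologic therapy. No sentence specifies complications as a contrast by adherence. It is still the natural reading, because adherence is the factor under study and complication rates are listed endpoints.

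The text gives no visit schedule, no common post-discharge assessment and no window fixed from the operation. A later analysis plan could not fully repair this if the data were not collected.

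**Conclusion.** The point holds as a risk of differential detection. It does not show that a lower minor-complication rate with high adherence would be an artefact. The bias favours high adherence if two conditions hold: stay is shorter with high adherence, as the Background leads one to expect, and mild events are detected less completely after discharge than in hospital, which is plausible but not shown.

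The size is unknown. Under the stated assumptions it runs from nil, through a negligible effect at 90% detection, to one large enough to produce a nominally significant result at 40%. Minor complications, grade I above all, are the part affected; events of grade III or higher are less open to it because they require intervention. Low to moderate priority, as this concerns a secondary endpoint.

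**What to change.** 1. Record the onset day of each complication, if the database does not already hold it (its form is not shown).
2. Count complications in a fixed window from the operation that every patient completes. Eight weeks is one option: follow-up that runs its full 8 weeks from discharge covers it.
3. Ask every patient the same complication questions at an existing contact, either the outpatient visit or the 6-week questionnaire. The window should not extend past that contact: the 6-week contact supports a 6-week window, while 8 weeks needs a clinic contact at its end.
4. Report minor complications separately for before and after discharge.
5. As a sensitivity analysis, compare minor complications with onset in an early window when nearly all patients of both groups are still in hospital.
6. Present grade III or higher beside the minor rate, as the comparison less open to detection bias. It should support the minor-complication comparison, not replace it, since dropping that comparison would give up information.

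The cost is one date field, a short question set at a contact already planned, and a change of analysis wording. Slightly fewer events are counted, because those after the fixed window drop out, and the early-window analysis uses fewer still. These steps do not resolve the reverse causation between complications and stay, which should be stated when the results are interpreted.
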